### **3.4. Baseline Variables**

#### **3.4.1. Baseline Definition**

Day 1 is defined as the day of the vaccination for Substudy A and as the day of the first dose for Substudy B. Measurements or samples collected prior to the vaccination on Day 1 are considered the baseline data for the assessments.

#### **3.4.2. Demographics, Baseline, and Medical History**

The demographic variables that will be collected include sex, race, ethnicity, and date of birth. Age at the time of vaccination (in years) will be derived based on birthday. For example, if the vaccination date is 1 day before the participant’s 60th birthday, the participant is 59 years of age.

Medical history of clinical significance will be collected and categorized according to the current version (at the time of reporting) of MedDRA. The prespecified medical conditions listed below are recorded for all participants on the CRF of the prespecified significant medical history, otherwise specified.

For Substudy A, the following will be derived:

- Resident of nursing home/long-term care facility
- Pulmonary conditions
  - COPD

- Asthma
- Other lung disease
- Cardiovascular conditions
  - CHF
  - CAD
  - Other heart disease
- Diabetes mellitus
- Other
  - Other metabolic disease
  - Liver disease
  - Renal disease
  - Neurologic disease
  - Hematologic disease

For Substudy B only, the following will be derived based on the CRF of participant characteristics – immunocompromised criteria:

- Having known advanced NSCLC
- Currently undergoing maintenance hemodialysis treatment secondary to end-stage renal disease
- Active immunomodulator therapy for an autoimmune inflammatory disorder at a stable dose
- Receiving an SOT at least 3 months (84 days) prior to enrollment and with no acute rejection episodes within 2 months (60 days) prior to enrollment

### **3.4.3. E-Diary Completion**

An e-diary will be considered transmitted if any data for the local reactions and systemic events are present for any day. If all data are missing for all items (local reactions and systemic events) on the e-diary for all 7 days after vaccination, then the e-diary will be considered not transmitted. An e-diary will be considered transmitted for a given day if any data are present for that day. The following variables will be derived:

---

- E-diary data transmitted on each day from Day 1 through Day 7.
- E-diary data transmitted on any day from Day 1 through Day 7.
- E-diary data transmitted on both Day 1 and Day 2.
- E-diary data transmitted from Day 1 through Day 3.
- E-diary data transmitted from Day 1 through Day 4.
- E-diary data transmitted from Day 1 through Day 5.
- E-diary data transmitted from Day 1 through Day 6.
- E-diary data transmitted for all 7 days.

### **3.4.4. Nonstudy Vaccines**

Any nonstudy vaccinations received from 28 days prior to study enrollment through the conclusion of study participation will be collected.

Nonstudy vaccinations will be categorized according to the latest version (at the time of reporting) of the WHODrug Dictionary.

## **3.5. Safety Endpoints**

### **3.5.1. Vital Sign Data**

The temperature collected before the vaccination will only be used to assess any potential protocol deviations for vaccination temporary delay. Therefore, it will not be included as a baseline variable.

### **3.5.2. Adverse Events**

A 3-tier approach will be used to summarize AEs. Under this approach, AEs are classified into 1 of 3 tiers. Different analyses will be performed for different tiers (refer to [Section 6.6.1](#)).

- Tier 1 events: These are prespecified events of clinical importance and are maintained in a list in the product's safety review plan. Guillain-Barre syndrome, acute polyneuropathy, atrial fibrillation (occurring from vaccination through the 1-month follow-up visit), preterm delivery (occurring from vaccination through the end of the study), preterm birth (occurring from vaccination through the end of the study), and hypertensive disorders of pregnancy (occurring from vaccination through the end of the study) will be included as the Tier 1 event analysis for RSVpreF. The derivation for Guillain-Barre syndrome and acute polyneuropathy is from Day 1 through Day 43 after vaccination (Day 1 is the vaccination day) for Substudy A and is from Day 1 of initial vaccination through Day 43 of the last vaccination for Substudy B. The RSV program Tier 1 list of MedDRA PTs is maintained by the safety risk lead in the CAETeLiSt and is

referenced in the safety surveillance review plan for the program. The current list of Tier 1 events referenced by this study for RSVpreF should be confirmed to ensure that appropriate Tier 1 events will be used to produce final tables/graphs before conducting an analysis.

Note that the denominator for calculating the preterm delivery, preterm birth, and hypertensive disorders of pregnancy would be the number of pregnant women in the corresponding substudy.

- Tier 2 events: These are events that are not Tier 1 but are “common.” A MedDRA PT is defined as a Tier 2 event if its incidence is at least 1% in any study intervention group. As there is no placebo group in Substudy B, Tier 2 event analysis is not defined for this substudy.
- Tier 3 events: These are events that are neither Tier 1 nor Tier 2 events.

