Follow-up is conducted to obtain general information on the pregnancy and its outcome for all EDP reports with an unknown outcome. The investigator will follow the pregnancy until completion (or until pregnancy termination) and notify Pfizer Safety of the outcome as a follow-up to the initial report. In the case of a live birth, the structural integrity of the neonate can be assessed at the time of birth. In the event of a termination, the reason(s) for termination should be specified and, if clinically possible, the structural integrity of the terminated fetus should be assessed by gross visual inspection (unless preprocedure test findings are conclusive for a congenital anomaly and the findings are reported).

Abnormal pregnancy outcomes are considered SAEs. If the outcome of the pregnancy meets the criteria for an SAE (ie, ectopic pregnancy, spontaneous abortion, intrauterine fetal demise, neonatal death, congenital anomaly), the investigator should follow the procedures for reporting SAEs. Additional information about pregnancy outcomes that are reported to Pfizer Safety as SAEs follows:

- Spontaneous abortion including miscarriage and missed abortion should be reported as an SAE;
- Neonatal deaths that occur within 1 month of birth should be reported, without regard to causality, as SAEs. In addition, infant deaths after 1 month should be reported as SAEs when the investigator assesses the infant death as related or possibly related to exposure to the study intervention.

Additional information regarding the EDP may be requested by the sponsor. Further follow-up of birth outcomes will be handled on a case-by-case basis (eg, follow-up on preterm infants to identify developmental delays). In the case of paternal exposure, the investigator will provide the participant with the Pregnant Partner Release of Information Form to deliver to his partner. The investigator must document in the source documents that

the participant was given the Pregnant Partner Release of Information Form to provide to his partner.

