8.4.8. Adverse Events of Special Interest

The following events are considered AESIs in Substudy A and Substudy B:

- Diagnosis of Guillain-Barre syndrome
- Diagnosis of acute polyneuropathy without an underlying etiology
- Diagnosis of atrial fibrillation
- Preterm delivery (delivery at <37 0/7 weeks' gestation)
- Diagnosis of a hypertensive disorder of pregnancy

Details of the AESIs listed above are further defined in the investigator site file.

All AESIs must be reported as an AE or SAE following the procedures described in Sections [8.4.1](#) through [8.4.4](#) from the time the participant provides informed consent through the end of study participation. An AESI is to be recorded as an AE or SAE on the CRF. In addition, an AESI that is also an SAE must be reported via PSSA or using the Vaccine SAE Report Form.

AESIs are examined as part of routine safety data review procedures throughout the clinical trial and as part of signal detection processes. Should an aggregate analysis indicate that these prespecified events occur more frequently than expected, eg, based on epidemiological data, literature, or other data, then this will be submitted and reported in accordance with Pfizer's safety reporting requirements. Aggregate analyses of safety data will be performed on a regular basis per internal SOPs.

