10.7.1.3. Schedule of Activities: Substudy A

Adults ≥ 18 to <60 years of age at high risk of RSV disease

Visit Number	101	102	103
Visit Description	Vaccination	1-Month Follow-Up	6-Month Safety Follow-Up
Visit Window (Days)	Day 1	28 to 35 Days After Vaccination at Visit 101	175 to 189 Days After Vaccination at Visit 101
Type of Visit	Clinic	Clinic	Telephone or Clinic
Obtain informed consent	X		
Assign single participant number	X		
Obtain demography and significant medical history data	X		
Record current/former tobacco usage	X		

Visit Number	101	102	103
Visit Description	Vaccination	1-Month Follow-Up	6-Month Safety Follow-Up
Visit Window (Days)	Day 1	28 to 35 Days After Vaccination at Visit 101	175 to 189 Days After Vaccination at Visit 101
Type of Visit	Clinic	Clinic	Telephone or Clinic
Perform clinical assessment, including respiratory rate (and physical examination if deemed necessary)	X		
Collect nonstudy vaccine information	X	X	X
Collect prohibited medications and treatments	X	X	X
Confirm inclusion and exclusion criteria	X		
Obtain prevaccination temperature	X		
Review temporary delay criteria	X		
Assign randomization number	X		
Obtain blood sample for antibody assessment	~20 mL	~20 mL	
Administer study intervention	X		
Assess acute reactions for at least 30 minutes after study intervention administration	X		
Dispense measuring device and digital thermometer	X		
Provide e-diary training on daily reactogenicity questionnaire	X		
Assist the participant in downloading the study application onto his or her own device or issue a provisioned device if required for e-diary	X		
Review reactogenicity e-diary data (daily review is optimal during the active diary period)	X		
Review ongoing reactogenicity e-diary symptoms and obtain stop dates		X	
Collect the provisioned device or assist the participant with removing the study application from his or her own personal device		X	
Record AEs as appropriate	X	X	
Collect AESIs, SAEs, and NDCMCs as appropriate	X	X	X

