## 6.6. Safety Summaries and Analyses

### 6.6.1. Adverse Events

For all of the AEs categorized in [Section 3.1.3.3](#), each individual AE will be categorized by MedDRA and descriptively summarized by vaccine group.

A 3-tier approach will be used to summarize AEs. Under this approach, AEs are classified into 1 of 3 tiers ([Section 3.5.2](#)). For both Tier 1 and Tier 2 events, 2-sided 95% CIs, for the difference between the active vaccine and placebo groups in the percentage of participants reporting the events based on the Miettinen and Nurminen method, will be provided. In addition, for Tier 1 events, the asymptotic p-values will also be presented for the difference between groups in the percentage of participants reporting the events, based on the same test statistic and under the assumption that the test statistic is asymptotically normally distributed. AE displays will be sorted in descending order of point estimates of risk difference within the SOC. For Substudy A, the analysis of Tier 1 events is planned for comparing the RSVpreF vaccination group and the placebo vaccination group. For Substudy B, the analysis of Tier 1 events will be compared with the background rate that had similar population characteristics, considering no placebo group was included in Substudy B.

It should be recognized that most studies are not designed to reliably demonstrate a causal relationship between the use of a pharmaceutical product and an AE or a group of AEs. Except for select events in unique situations, studies do not employ formal adjudication procedures for the purpose of event classification. As such, safety analysis is generally considered an exploratory analysis and its purpose is to generate hypotheses for further investigation. The 3-tier approach facilitates this exploratory analysis.

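### The Tier 1 preterm rate counts deliveries only to study end but divides by every pregnant woman, so it is biased low

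*SAP*

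**What the plan says.** SAP 3.5.2 lists the Tier 1 events with their counting windows. Preterm delivery enters as "preterm delivery (occurring from vaccination through the end of the study"). Preterm birth has the same window, and so do "hypertensive disorders of pregnancy (occurring from vaccination through the end of the study"). For these three events the denominator "would be the number of pregnant women in the corresponding substudy". Nothing restricts it to pregnancies that have ended or were followed long enough.

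Protocol 8.4.8 defines the event as "Preterm delivery (delivery at <37 0/7 weeks' gestation") and has AESIs reported "from the time the participant provides informed consent through the end of study participation". In Substudy A the last contact falls "175 to 189 Days After Vaccination at Visit 101" (Protocol 10.7.1.3). In Substudy B it falls 175 to 189 days after the second dose, which is given 28 to 35 days after the first (Protocol 10.8.1.3). Protocol 4.4, however, ends each substudy at the last participant's last visit.

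Protocol 8.4.5.1 is less clear-cut. It says pregnancy details are collected until the study ends, but also: "The investigator will follow the pregnancy until completion (or until pregnancy termination") and report the outcome to the sponsor's safety group.

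On the comparison, SAP 6.6.1 states: "For Substudy A, the analysis of Tier 1 events is planned for comparing the RSVpreF vaccination group and the placebo vaccination group". Substudy B has no control arm, and its Tier 1 events are set against a background rate.

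**The concern.** A pregnancy still ongoing when the window closes adds one to the denominator and cannot add to the numerator, whatever its eventual outcome. Such pregnancies are foreseeable: neither substudy's exclusion list names pregnancy, and the contraceptive guidance appendix is marked not applicable.

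The outcome matters to the sponsor. The SAP version history attributes the Tier 1 additions to a regulator's request. The risk table in Protocol 2.3.1 reports preterm birth of 5.7% versus 4.7% in the maternal trial. It describes this as not a meaningful overall imbalance, but notes a numerical one in upper-middle-income countries. It adds that most preterm and hypertensive events came more than 30 days after vaccination. A window that drops late outcomes weakens the table meant to watch for this event.

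**Working it through.** The documents give no expected number of pregnancies, preterm rate or power for these events, so there is no stated figure to reproduce. The check is date arithmetic plus a simple model.

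**Inputs.** Follow-up F after the single dose in Substudy A: 175 to 189 days. Follow-up after dose 1 in Substudy B: 28 + 175 = 203 to 35 + 189 = 224 days. Preterm limit: 37 × 7 = 259 days of gestation. Assumed: gestational age = days since conception + 14.

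**Gestation at last contact, conception on the day of vaccination.**
- Substudy A: 175 + 14 = 189 days (27w0d) to 189 + 14 = 203 days (29w0d).
- Substudy B, from dose 1: 217 days (31w0d) to 238 days (34w0d).

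Later conceptions reach less.

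**Gestation needed at vaccination to be observed to 37w0d.**
- Substudy A: 259 − 189 = 70 days (10w0d) to 259 − 175 = 84 days (12w0d).
- Substudy B, from dose 1: 259 − 224 = 35 days (5w0d) to 259 − 203 = 56 days (8w0d).

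Women at or beyond these points have their whole preterm window observed.

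**Share of preterm deliveries after on-study conception that can be counted, if the window ends at the participant's last contact.** Assume conception uniform over follow-up and preterm deliveries between 140 and 259 days of gestation (a span of 119 days). The earliest countable delivery is 140 − 14 = 126 days after conception. With a flat gestational-age distribution the share is (F − 126)² / (2 × 119 × F). With a density rising linearly to 37 weeks it is (F − 126)³ / (3 × 119² × F).

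| F (days) | Flat | Late-weighted |
|---|---|---|
| 175 (A) | 49²/(2×119×175) = 5.8% | 49³/(3×119²×175) = 1.6% |
| 189 (A) | 63²/(2×119×189) = 8.8% | 63³/(3×119²×189) = 3.1% |
| 203 (B) | 77²/(2×119×203) = 12.3% | 77³/(3×119²×203) = 5.3% |
| 224 (B) | 98²/(2×119×224) = 18.0% | 98³/(3×119²×224) = 9.9% |

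**If the window ends at the last participant's last visit.** More is counted, by an amount that depends on the enrolment span, which the documents do not give. For Substudy A (F = 189, uniform enrolment, outcomes entered until then), simulation gives these flat/late-weighted shares:
- 60 days: 20%/11%
- 120 days: 35%/25%
- 180 days: 50%/40%
- 365 days: 75%/70%

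**Effect on the contrast in Substudy A.** With each arm's own denominator and a countable share s, true rates p1 and p0 appear as s·p1 and s·p0. For illustration, s = 9% turns 10% versus 5% into 0.90% versus 0.45%. The ratio stays 2 and the difference falls from 5 to 0.45 points. If p1 = p0, the expected difference stays 0.

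**Effect in Substudy B.** The study rate is s·p and no concurrent arm shares the factor s. Against a background rate covering whole pregnancies, equal risk would look like a lower risk after vaccination.

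**The case against.** A reader might infer that the between-arm comparison itself is distorted, because the denominator is written by substudy and allocation is 2:1. If both arms shared one denominator, an equal risk of 5% would appear as 3.3% versus 1.7%. The documents do not support that reading. SAP 6.6.1 takes a difference in percentages between vaccine groups by Miettinen-Nurminen, which SAP 5.2.1 describes as a between-group method. SAP 6.1.4.1 presents n, N and % for each vaccine group. The natural sense is that pregnant women replace all participants as the base, within each group. The wording merits a clarification, no more. Nor does truncation favour one arm: Substudy A is randomised and double-blind, with the same window in both arms.

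A reader might also infer that the plan hides preterm events. It does not. Pregnancies are followed to completion and reported to the sponsor's safety group, AESIs have ongoing aggregate review (Protocol 8.4.8), and a DMC monitors safety (Protocol 10.1.5.1). Only this table is truncated, and SAP 6.6.1 describes safety analysis as generally exploratory.

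Finally, the 27-to-29-week ceiling requires that the window close at the participant's own last contact. Protocol 8.4.8 points that way for AESI collection and Protocol 4.4 points the other way. This objection stands in part: the size of the loss is uncertain until the term is defined. The mismatch between numerator and denominator remains under either reading.

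**Conclusion.** The point holds as a downward bias in the preterm rate among pregnancies conceived on study. With a participant-level window, about 2% to 9% of preterm deliveries after on-study conception would be counted in Substudy A and 5% to 18% in Substudy B. With a substudy-level window the Substudy A share is about 11% to 75% for enrolment spans of 60 to 365 days. These ranges rest on the assumed gestational dating, uniform conception and the two delivery distributions. Women already 10 to 12 weeks pregnant at vaccination in Substudy A are unaffected.

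In Substudy A the result is attenuation and lost events, not a spurious difference. In Substudy B there is a real risk of false reassurance if the background rate covers whole pregnancies. No success criterion depends on this analysis, and few pregnancies are likely (an assumption). The practical impact is therefore limited, but the correction is cheap and should be made.

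**What to change.** In SAP 3.5.2, with a matching sentence in 6.6.1:

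- **Preterm denominator.** For preterm delivery and birth, use the pregnancies that, by gestational dating, would have reached 37 0/7 weeks by the data cut-off, whether or not they have already delivered. Take their outcomes from the follow-up to completion in Protocol 8.4.5.1. A rule of known delivery date or 37 weeks reached would not do: before all pregnancies end, it keeps an early preterm delivery and drops an ongoing pregnancy of the same gestational age, which inflates the rate.
- **Remaining pregnancies.** Report separately the number still ongoing or not yet dated to 37 weeks at cut-off, and update the table when their outcomes are known.
- **Substudy B.** Use a background rate over the same gestational window, or label the study rate as truncated.
- **Clarifications.** State that the denominator is pregnant participants in each vaccine group, and define the end of the study for this table.

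The cost is SAP wording and some data work. Protocol 10.2.3 keeps pregnancy exposures without an AE or SAE out of the CRF, so outcomes in the safety database must be reconciled with the clinical database. An update table may be needed after the primary analysis. The outcome follow-up itself is already required.

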#### 4. ANALYSIS SETS (POPULATIONS FOR ANALYSIS)

Data for all participants will be assessed to determine if participants meet the criteria for inclusion in each analysis population prior to unblinding and releasing the database, and classifications will be documented per standard operating procedures.

For the purposes of analysis, the following analysis sets are defined:

Participant Analysis Set	Description	Applicable Analysis
Enrolled population	All participants who have a signed ICD.	Study conduct such as participant disposition.
Randomized population	All enrolled participants who are assigned a randomization number in the IRT system.	Immunogenicity analysis population disposition.
Safety population	
All enrolled participants who received the study intervention.
 
For Substudy B, the safety population will be defined for each dose as follows:
 
 
• Safety population for Dose 1: The participants who received the first dose of RSVpreF.
 
• Safety population for Dose 2: The participants who received 2 doses of RSVpreF.
 
	AE/SAE analysis.

Participant Analysis Set	Description	Applicable Analysis
E-diary safety population	
All participants who received the study intervention with at least 1 day of e-diary data transmitted.
 
Note: If all participants have at least 1 day of e-diary data transmitted, this will be the same as the safety population.
 
For Substudy B, the 2 doses will be as follows:
 
The e-diary safety population for Dose 1: The participants who received the first dose of RSVpreF and have at least 1 day of e-diary data transferred during the Dose 1 e-diary collection period.
 
The e-diary safety population for Dose 2: The participants who received 2 doses of RSVpreF and have at least 1 day of e-diary data transferred during the Dose 2 e-diary collection period.
	Local reactions and systemic events analysis

Defined Analysis Set	Description	Applicable Analysis
Evaluable immunogenicity population	
This population will be defined for Substudy A and Substudy B separately.
 
For Substudy A, it includes all participants who meet the following criteria:
 
 
• Are eligible for Substudy A.
 
• Received the study interventions (RSVpreF or placebo) to which they were randomized.
 
• Have the 1-month postvaccination blood collection 27-42 days after vaccination.
 
• Have at least 1 valid and determinate assay result 1 month after vaccination.
 
• Have no major protocol violations from vaccination through the 1-month postvaccination blood draw.
 
	Primary analysis population for immunogenicity endpoints (primary/secondary).

Defined Analysis Set	Description	Applicable Analysis
	
For Substudy B, it includes all participants who meet the following criteria:
 
 
• Are eligible for Substudy B.
 
• Received 2 doses of RSVpreF.
 
• Have the blood collection for 1 month after the last dose to be 27-42 days after the second dose of RSVpreF.
 
• Have at least 1 valid and determinate assay result 1 month after vaccination (1 month after the second dose of RSVpreF).
 
• Have no major protocol violations from vaccination through the 1-month postvaccination blood draw (1 month after the second dose of RSVpreF).
 
	
mITT immunogenicity population	All participants who are randomized and have at least 1 valid and determinate assay result at any time point after receiving the study intervention.	Supplemental analysis on immunogenicity endpoints (primary/secondary).

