10.8.3. Objectives, Endpoints, and Estimands for Substudy B

Objectives	Endpoints	Estimands
Primary Safety	Primary Safety	Primary Safety

To describe the safety profile of RSVpreF as measured by the percentage of immunocompromised participants ≥ 18 years of age reporting local reactions, systemic events, AEs, and SAEs following study intervention administration.	
Local reactions (pain at the injection site, redness, and swelling)Systemic events (fever, nausea, diarrhea, vomiting, headache, fatigue, muscle pain, and joint pain)AEsNDCMCsSAEs	
In participants receiving study intervention:
 
The proportion of participants reporting local reactions within 7 days following each study intervention administration.The proportion of participants reporting systemic events within 7 days following each study intervention administration.The proportion of participants reporting AEs through 1 month following the last dose of study intervention administration.The proportion of participants reporting NDCMCs throughout the study.The proportion of participants reporting SAEs throughout the study.

Objectives	Endpoints	Estimands
Primary Immunogenicity	Primary Immunogenicity	Primary Immunogenicity

 To describe the immune responses elicited by RSVpreF in immunocompromised adults ≥ 18 years of age. 	RSV A and RSV B serum NTs	
In participants in compliance with the key protocol criteria (evaluable immunogenicity population):
 
 GMT of NTs for RSV A and RSV B at each blood sampling visit. GMFR of NTs for RSV A and RSV B from before vaccination to each postvaccination blood sampling visit.

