10.8.9.1.1. Estimands

The estimands corresponding to each primary, secondary, and exploratory objective (if any) are described in [Section 10.8.3](#).

The estimands to evaluate the immunogenicity objectives are based on the evaluable immunogenicity population ([Section 10.8.9.2](#)). These estimands estimate the vaccine effect in the hypothetical setting where participants follow the study schedules and protocol requirements as directed. Missing immunogenicity results will not be imputed, as MCAR is assumed.

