		
muscle pain, and joint pain).
 
 
• AEs.
 
• NDCMCs.
 
• SAEs.
 
	
systemic events within 7 days following each study intervention administration.
 
 
• The proportion of participants reporting AEs through 1 month following the last dose of study intervention administration.
 
• The proportion of participants reporting NDCMCs throughout the study.
 
• The proportion of participants reporting SAEs throughout the study.
 

Substudy B Primary Immunogenicity	
 
• To describe the immune responses elicited by RSVpreF in immunocompromised adults <math>\geq 18</math> years of age.
 
	RSV A and RSV B serum NTs.	
In participants in compliance with the key protocol criteria (evaluable immunogenicity population):
 
 
• GMT of NTs for RSV A and RSV B at each blood sampling visit.
 
• GMFR of NTs for RSV A and RSV B from before vaccination to each postvaccination blood sampling visit.
 

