### 2.2.1.2. Substudy B Primary Immunogenicity Estimands

The primary estimands for the primary immunogenicity objective will use the hypothetical strategy and evaluate the RSVpreF immune response of participants in Study C3671023 Substudy B without the intercurrent events. In other words, the immune response is estimated in the hypothetical setting where participants follow the study schedule and protocol requirements as directed. It includes the following 5 attributes:

- **Treatment condition:** RSVpreF received in Substudy B.
- **Population:** Participants as defined by the study inclusion/exclusion criteria for Substudy B.

- **Variables:** RSV serum NTs for subgroup A and subgroup B measured at 1 month after each dose of RSVpreF.
- **Intercurrent events:** The following intercurrent events could impact the interpretation or the measurement of the immune response:
  1. The participant did not receive the 2 RSVpreF doses in Substudy B.
  2. The participant did not meet the study inclusion criteria or did meet the exclusion criteria for Substudy B.
  3. Major protocol violations: The participant received a prohibited vaccine or treatment that may alter the immune response.
  4. Blood was taken outside an acceptable window for immunogenicity evaluation (<27 days or >42 days after the second dose of RSVpreF).

The clinical question of interest is to describe the immune response elicited from RSVpreF in immunocompromised adults ( $\geq 18$  years of age) among participants from this study's Substudy B, without any influence from any other immune-modifying vaccines and measured within a homogeneous time window. Therefore, all data after intercurrent events 1, 2, and 3, as well as all data at intercurrent event 4, if collected, will be excluded. Major protocol violations will be determined by clinical review.

- **Population-level summary:** GMT of NT before vaccination and 1 month after each dose, and GMFR of NT 1 month after each dose.

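### Substudy B: post-Dose-1 titers are analyzed in a set defined by Dose 2 events, and the post-Dose-1 draw has no analysis window (minor; inexpensive to improve)

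*SAP*

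**What the plan says.** **What is reported.** SAP 2.2.1.2 gives the population-level summary as "GMT of NT before vaccination and 1 month after each dose, and GMFR of NT 1 month after each dose". Protocol 10.8.3 lists "GMFR of NTs for RSV A and RSV B from before vaccination to each postvaccination blood sampling visit", and SAP 6.1.2.1 presents both statistics at each applicable visit.

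**Who is included.** The estimand table in SAP 2.2 begins "In participants in compliance with the key protocol criteria (evaluable immunogenicity population", and Protocol 10.8.9.1.1 says "The estimands to evaluate the immunogenicity objectives are based on the evaluable immunogenicity population". Protocol 9.3.1 applies the evaluable populations to all immunogenicity endpoints, and SAP 6.1.2.1 names the same set. For Substudy B, SAP 4 requires eligibility, two doses, a valid post-Dose-2 result, no major violation through that draw, and this timing: "Have the blood collection for 1 month after the last dose to be 27-42 days after the second dose of RSVpreF". Protocol 10.8.9.2 is parallel but leaves the window unspecified.

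**Which data are removed.** SAP 2.2.1.2 has its own rule: "Therefore, all data after intercurrent events 1, 2, and 3, as well as all data at intercurrent event 4, if collected, will be excluded". Event 4 reads "Blood was taken outside an acceptable window for immunogenicity evaluation (<27 days or >42 days after the second dose of RSVpreF".

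**Missing data and the supplement.** Protocol 10.8.9.1.1: "Missing immunogenicity results will not be imputed, as MCAR is assumed". Protocol 9.3.1 promises an mITT analysis if the mITT and evaluable sets differ enough in size, without saying how much. SAP 6.1.2.2 says only that it may be done.

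**The concern.** The endpoint is defined per dose but the analysis set is not. Blood for the post-Dose-1 titer is drawn at Visit 202 before Dose 2 is given, yet whether that titer counts depends on what happens afterwards. If people who miss Dose 2 or the later draw respond differently to Dose 1, the post-Dose-1 GMT and GMFR describe a selected group. In an immunocompromised population that is plausible, because eligibility is rechecked at Visit 202 and losing it is a listed reason for stopping study intervention (Protocol 7.1).

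There is a matching gap in the other direction. SAP 2.2.1.2 wants responses measured in a homogeneous time window, but its only analysis window is counted from the second dose. A badly timed post-Dose-1 sample can stay in while a well-timed one is removed for a later event.

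**Working it through.** The plan gives no figure to reproduce: Substudy B is descriptive (Protocol 10.8.9.1) and its size is not statistically based (Protocol 10.8.9.5). The check compares the texts and then illustrates the size.

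**1. The two rules side by side**, for someone with a valid post-Dose-1 titer:

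| Event | SAP 2.2.1.2 wording | Evaluable set (SAP 4) |
|---|---|---|
| Prohibited treatment after Visit 202 | titer kept; it precedes the event | participant removed |
| Post-Dose-2 draw outside 27-42 days | titer kept; only data at the event go | participant removed |
| Post-Dose-2 result missing or indeterminate | titer kept; not a listed event | participant removed |
| Dose 2 not given | kept if the event is dated to the missed dose; the text gives no date | participant removed |
| Post-Dose-1 draw late | kept unless clinical review calls it a major violation | same |

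The set is the stricter rule in the first three rows, and in the fourth on the natural reading. Neither rule covers the fifth.

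**2. One possible route to a late draw.** Licensed vaccines are allowed from 14 days after a dose (Protocol 10.8.6.7.2). A nonlive vaccine in the 14 days before vaccination is a delay criterion (Protocol 10.8.5.5), and the criteria are rechecked at Visit 202 before the draw (Protocol 10.8.8.4.2). A nonlive vaccine on day 22 after Dose 1 moves Dose 2 to day 22 + 14 = 36 or later, past the 35-day visit limit. One on day 29 moves it to day 29 + 14 = 43 or later, past the 42 days used after Dose 2. The protocol does not say whether the draw waits for the delayed dose.

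**3. Size of a selection effect.** Inputs:
- x, the share of those with a valid post-Dose-1 titer who are dropped. This is an assumption: no Substudy B rate is stated, and the only stated nonevaluable rate is about 10%, for Substudy A (Protocol 10.7.9.5).
- r, the GMT of those dropped relative to those kept (assumption).
- SD 1.1 on the natural-log scale, borrowed from Substudy A (Protocol 10.7.9.5).
- n = 200 overall and about 100 per age group, taking everyone to have a valid post-Dose-1 titer.

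If those kept have mean log titer m, the mean over everyone is (1 - x)m + x(m + ln r) = m + x ln r. So GMT(kept)/GMT(all) = r^(-x).

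- r = 1: ratio 1, no bias.
- x = 10%: 0.5^(-0.10) = 1.072; 2^(-0.10) = 0.933.
- x = 20%: 0.5^(-0.20) = 1.149; 2^(-0.20) = 0.871.

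**4. Against sampling error.** The 95% CI half-width factor is exp(t(0.975, n-1) × 1.1/√n).

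- Overall: n = 180 gives 1.176; n = 160 gives 1.187.
- Per age group: n = 90 gives 1.259; n = 80 gives 1.277.

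Each shift in step 3 is smaller than the matching half-width. The two are equal where x ln 2 = t × 1.1/√(n₀(1 - x)). For n₀ = 200 this gives x = 0.257; for n₀ = 100, x = 0.416.

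**5. Precision lost if MCAR holds.** The log-scale CI widens by √(200/180) = 1.054 at x = 10% and √(200/160) = 1.118 at x = 20%. The age-group ratios are the same. These are upper bounds, because some people excluded now would also fail a Dose 1 set.

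**The case against.** **Which set governs is settled.** A reader might infer from SAP 2.2.1.2 and SAP 4 that two programmers could legitimately build different post-Dose-1 tables. The documents do not support that. Protocol 9.3.1 assigns the evaluable population to all immunogenicity endpoints, and SAP 6.1.2.1 lists that set alongside the data exclusions, so the set is applied first. For the same reason it does not follow that Substudy B seroresponse has no analysis set because SAP 6.3.1 names none. What stands is that the estimand wording is looser than the set that governs.

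**The set fits the regimen.** The hypothetical estimand concerns people who follow the schedule, which has two doses, and Protocol 10.8.4.3 gives assessing a second dose as the rationale. Using the same people at each visit also suits comparing the doses. That supports keeping the two-dose set for the comparison. It does not require the post-Dose-1 summary to depend on later events.

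**There is a supplement.** A reader might treat the mITT analysis as purely optional. Under Protocol 9.3.1 it will be done if the size difference is large enough, and heavy loss is the case that would trigger it. Exclusions are also tabulated with reasons (SAP 6.5.2). But the trigger is not quantified, and the mITT set supplies no Dose 1 window. SAP 4 defines that set by randomization, which might suggest it is empty in a single-arm substudy. Protocol 10.8.9.2 defines it by receipt of study intervention, so this is an editorial slip.

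**Late draws are not shown to be likely.** This is fair: the delay criteria postpone the dose, and the draw may still occur on time. The absence of a rule remains.

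**Conclusion.** The point holds as a minor, inexpensive improvement. Valid post-Dose-1 titers are excluded for later events, the set is stricter than the SAP 2.2.1.2 wording, and the post-Dose-1 draw has no analysis window. Confidence is high on these textual gaps only.

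No test or prespecified decision is affected. Under MCAR the cost is precision: log-scale CIs at most about 5% wider at 10% dropped and 12% wider at 20%. If MCAR fails, the direction and size of bias are unknown. With a two-fold titer difference, about 26% overall or 42% of an age group would have to be dropped before the shift matched the CI half-width.

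A reader might infer a material overstatement of the Dose 1 response. A four-fold deficit in those dropped would give 0.25^(-0.20) = 1.32-fold at 20% dropped and 0.25^(-0.30) = 1.52-fold at 30%, both beyond sampling error. Nothing in the documents supports a difference or a loss of that size, so these figures do not raise the severity.

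**What to change.** 1. Add a Dose 1 evaluable set for Substudy B in SAP 4: eligible; received Dose 1; valid post-Dose-1 result drawn before Dose 2 and within an analysis window stated by the sponsor; no major violation through that draw. SAP 4 already defines per-dose safety and e-diary sets for this substudy.
2. Use it for post-Dose-1 GMT, GMFR and seroresponse.
3. Make intercurrent events 1 and 4 in SAP 2.2.1.2 dose-specific, and align SAP 2.2 and 4 and Protocol 10.8.3, 10.8.9.1.1 and 10.8.9.2 with that wording.
4. Keep the two-dose set for post-Dose-2 results and the paired Dose 1 versus Dose 2 comparison.
5. Editorial: use the Protocol 10.8.9.2 mITT definition in the SAP for Substudy B.

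**Cost.** SAP wording and matching protocol lines, through an amendment if the change is judged major under Protocol 9 and SAP 2. Extra post-Dose-1 tables are needed, including the subgroups in SAP 6.4 (age, four immunocompromised groups, race, ethnicity, sex) and the population and exclusion summaries in SAP 6.5. The n will differ by visit, so the paired two-dose results should be shown alongside.
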